4.2.2.2 Restrictions on diet and life style

At the beginning of the Run-in period, patients will receive diet and exercise counselling by a diet specialist or trained staff member. The counselling will be based on local diet recommendations and should include a food log/intake booklet. The patients will be reminded to follow the agreed diet and exercise plan at every visit. A food intake booklet will be provided as a tool but site specific tools could also be used. Record of the actual food intake over a time of three consecutive days before the clinic visit is requested at regular intervals as indicated in the [Flow chart](#). The food intake booklet will remain with the patient and no data will be transferred to the eCRF. The respective procedure for illiterate patients (if included) is described in [Appendix 10.1](#).

Women of child-bearing potential must continue to practice an acceptable method of birth control (in accordance with the trial exclusion criteria Section 3.3.3) throughout the duration of the study.

Patients should also not take an investigational drug in another trial within 30 days prior to intake of study medication in this trial.

There are no other restrictions on diet and lifestyle.

4.3 TREATMENT COMPLIANCE

Patients will be asked to bring all trial medication containers (with or without any remaining tablets) with them to each trial visit. The tablets will be counted by the Investigator or study nurse and compliance will be calculated according to the formula:

$$\text{Compliance(\%)} = \frac{\text{Number of tablets actually taken since last tablet count}}{\text{Number of tablets which should have been taken in the same period}} \times 100\%$$

Compliance during the placebo run-in period should be between 80% and 120%. If compliance is outside this range, the patient should be carefully interviewed and, if necessary,

Proprietary confidential information.

© 2016 Boehringer Ingelheim International GmbH or one or more of its affiliated companies. All rights reserved.

This document may not - in full or in part - be passed on, reproduced, published or otherwise used without prior written permission.

re-informed about the purpose and the conduct of the trial. Unreliable patients should not be randomised at the discretion of the Investigator.

Compliance during the double-blind treatment period should also be between 80% and 120%. Patients who are not compliant according to this definition should be carefully interviewed and re-informed about the purpose and the conduct of the trial.

A comment should be registered in the eCRF (Study medication compliance page) for any patient that has taken <80% study medication or who has not taken study medication since the last visit. Any time a patient is off study medication for > 7 consecutive days this should be also registered in the eCRF on the Study Med Stop page. Starting and stopping study medication is allowed in this trial.

Patients who forget to return trial medication and empty containers should be reminded to bring them to their next visit. Compliance for patients who forget to return trial medication in two consecutive visits should be calculated per the discretion of the Investigator and this should be reflected on the clinical history.

5. VARIABLES AND THEIR ASSESSMENT

5.1 EFFICACY - PHARMACODYNAMICS

5.1.1 Endpoints of efficacy

The primary endpoint in this study is change from baseline in HbA1c at 24 weeks of treatment. Throughout the study protocol, the term "baseline" refers to the last observation prior to randomisation of the patient.

Key secondary endpoints:

- Change from baseline in mean 24-hour ambulatory SBP at 12 weeks of treatment.
- Change from baseline in mean trough ambulatory SBP at 12 weeks of treatment.
- Change from baseline in body weight at 24 weeks of treatment
- Change from baseline in trough seated SBP at 12 weeks of treatment.

Other secondary endpoints are:

- Change from baseline in mean 24-hour ambulatory DBP at 12 weeks of treatment.
- Change from baseline in trough seated SBP at 24 weeks of treatment
- Change from baseline in mean 24-hour ambulatory SBP at 24 weeks of treatment.
- Change from baseline in mean 24-hour ambulatory DBP at 24 weeks of treatment.
- Change from baseline in trough seated DBP at 12 weeks of treatment
- Change from baseline in trough seated DBP at 24 weeks of treatment

[REDACTED]

[REDACTED]

[REDACTED]

[REDACTED]

Proprietary confidential information.

© 2016 Boehringer Ingelheim International GmbH or one or more of its affiliated companies. All rights reserved.

This document may not - in full or in part - be passed on, reproduced, published or otherwise used without prior written permission.

[REDACTED]

5.1.2 Assessment of efficacy

HbA1c

Blood samples for the determination of HbA1c at the central laboratory will be taken. At the screening Visit 1, the blood sample can be taken at any time during the visit. At all other Visits, the blood samples should be drawn before breakfast and before trial drug administration. The samples will be analysed at a central laboratory or its affiliates having a National Glycohaemoglobin Standardisation Program Level I certificate. Further details about sample handling, shipment, and assay procedures can be found in the ISF (Lab manual).

Fasting plasma glucose

Blood samples for the determination of FPG at the central laboratory will be taken after an overnight fast. The samples should be taken before breakfast and before trial drug administration. The samples will be measured at a central laboratory using validated assays. Further details about sample handling and shipment can be found in the ISF (Lab manual).

Ambulatory blood pressure monitoring (ABPM)

ABPM will be performed in parallel using the ABPM device. A blood pressure monitoring device will be provided for ABPM recordings.

On the mornings when the ABPM device will be applied (Visits 2.2, 5.1 and 7.1), patients should arrive at approximately half an hour prior to medication intake to allow additional time for ABPM procedures, so that dosing of medication occurs as close as possible to patient daily dosing time. It is important that the dosing time for the baseline ABPM (Visit 2.2) is the same as the dosing time for the 12 and 24 week ABPM (Visits 5.1 and 7.1). In addition, for collection of Visit 2.2, 5.1 and 7.1 ABPM, the daytime and night time activities of the patient during the 24 hours should be similar. For example, if the baseline ABPM falls on a normal workday, then the final ABPM measurement should be scheduled for a normal workday, not a weekend or vacation day. Measurements of BP using the monitor should be taken from the same arm that is used to measure seated BP.

The ABPM device will be programmed to measure blood pressure every 20 minutes throughout the day and night to measure BP. Patients should be advised not to move the arm during each blood pressure measurement and will also be given instructions concerning interruption of measurement in case of malfunction of the device or repositioning of the cuff if it slips.

At each ABPM visit (Visits 2.2, 5.1 and 7.1), patients are to come to the clinic fasting and the following procedure will be performed. The ABPM device will be attached to the patient and test readings will be taken to check if the device is working properly prior to medication intake. The first test reading is the Beginning of Test reading. Once it has been confirmed that the monitor is properly functioning, study medication will be administered. Record the time the medication was administered and the time the monitor was prompted to take the Beginning of Test reading. The next day when the patient returns to the clinic, the monitor will be prompted to take a Conclusion of Test reading. The device will then be removed and the time of the Conclusion of Test will be recorded. This should be done within 23:30-24 hours of starting monitor.

After each ABPM session, the data from the device is to be downloaded and assessed to determine if the session was successful.

At Visit 2.2 only, if the first session does not pass quality criteria or the mean ABPM SBP is outside the required range, the session should be repeated. Only one repeat session will be permitted. It is important to remember to record the 24-hour mean SBP which is displayed at the bottom of the quality compliance (QC) results. The 24-hour mean SBP at this visit together with a successful session determines eligibility for randomization.

After the removal of the monitor and prior to study medication intake, the patient will be allowed rest for 15 minutes and a seated BP measurement (trough BP) will be taken. The patient will then be given study medication. The time for each of the seated BP measurement, medication intake, and the beginning and conclusion of the 24 hours ABPM readings must be recorded.

Further details on the procedure for BP measurement utilizing ABPM device can be found in the ISF.

Proprietary confidential information.

© 2016 Boehringer Ingelheim International GmbH or one or more of its affiliated companies. All rights reserved.

This document may not - in full or in part - be passed on, reproduced, published or otherwise used without prior written permission.

Blood pressure (seated SBP and DBP)

SBP and DBP as well as pulse rate (electronically or by palpation, count for 1 minute) will be measured after 2 minutes of rest in the seated position. The BP measurement should be performed three times at each time point and the mean value of these measurements will be calculated by RDC. Further details on the procedure for BP measurements are given in [Appendix 10.2](#).

Trough mean BP value is the mean of these three measurements on the day of the clinic visit before study drug intake.

Weight 

Weight measurements should always be done on the same scales for one patient. In order to get comparable body weight values, it should be performed in the following way:

- fasting (except for the Screening Visit),
- after the urine sampling (weight after bladder voiding),
- shoes and coat/jackets should be taken off
- Pockets should be emptied of heavy objects (i.e. keys, coins etc).

Proprietary confidential information.

© 2016 Boehringer Ingelheim International GmbH or one or more of its affiliated companies. All rights reserved.

This document may not - in full or in part - be passed on, reproduced, published or otherwise used without prior written permission.

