- If the first ABPM attempt was unsuccessful (failed QC and/or the mean ABPM SBP is outside the required range), repeat it within 2 days. Patients having two unsuccessful baseline ABPM sessions should not be randomised and must be discontinued.
- If ABPM was successful, the patient is eligible for randomization and procedures for Visit 3 can be conducted on the same day after the ABPM device is removed and trough seated blood pressure measurement is taken. If conducted on the same day, procedures for Visit 3 should be done prior to administering study medication.
- Allow the patient to rest for at least 15 minutes after the monitor is removed. Then take a seated blood pressure measurement. Record the time of this measurement. This should be done prior to administering study medication.
- For further instructions for ABPM measurements, please see [Section 5.1.2](#).
- Instruct patients NOT to take study medication on the morning of the next trial visit.

Patients who fail the run-in period following Visit 2 procedures should be registered as a screen failure in the IRT system.

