6.2.2 Treatment period

The treatment period is from Visit 3 to Visit 7.2. Patients will be dispensed medication at Visits 3, 4, and 5.2. Patients will receive a new kit number through the IRT system on each occasion. Assessments should be performed as mentioned in the [Flow Chart](#) and the respective protocol sections.

Throughout the treatment period, BP should always be measured before any blood samples are taken. For details regarding the correct method for measuring BP, please see [Appendix 10.3](#).

Visit 3 (Randomisation visit)

- Inclusion/exclusion criteria must be reviewed prior to randomization
- BP measurement and orthostatic blood pressure test should always be done before taking any blood sample.
- Collection of urine and blood for laboratory testing must be performed prior to administration of study medication.
- Collect returned run-in medication.
- Collect blood sample for PG evaluation after obtaining separate informed consent. PG sample should be collected for randomised patients only.
- Patients should be reminded about the importance of following the agreed diet and exercise plan. Patients should be given a food log to be completed for three consecutive days prior to Visit 4 as indicated in the Flow Chart.
- Provide HBGM equipment/supplies and instruct patient on the correct use of HBGM.

Proprietary confidential information.

- Instruct patient to perform a HBGM once weekly during the treatment period (more frequently if required by local authorities) in the fasted state and at any time the patient is symptomatic, i.e., experiences signs/symptoms of hyper or hypoglycemia. Instruct patient to contact site immediately if blood glucose reaches the limit described in [Section 4.2.1.](#)
- Once all visit procedures are conducted, contact the IRT system to randomise the patient and obtain medication kit numbers and dispense the medication to the patient.
- Administration first dose of study medication.
- Instruct patients NOT to take study medication on the morning of the next trial visit.

Visit 4

- BP should always be measured before taking any blood samples.
- Collection of urine and blood for laboratory testing must be performed prior to administration of study medication at each visit.
- Collect returned medication.
- New medication kit must be dispensed according to the [Flow Chart](#), and the IRT system must be contacted to obtain medication kit numbers to be dispensed.

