7.2 NULL AND ALTERNATIVE HYPOTHESES

Primary Hypotheses

The confirmatory analyses will compare empagliflozin to placebo. The following hierarchical multiple testing procedure will be used to evaluate superiority for the primary endpoint followed by the evaluation of superiority of the key secondary endpoints, while maintaining the overall probability of a type I error at 0.05. The primary endpoint of change from baseline to 24 weeks in HbA1c along with the key secondary endpoints change from baseline in mean 24-hour ambulatory SBP at 12 weeks of treatment, change from baseline in mean trough ambulatory SBP at 12 weeks of treatment, change from baseline in body weight in kg at week 24 of treatment, and change from baseline in trough seated SBP at 12 weeks of treatment, will be tested in the following pre-specified hierarchical sequence, to address issues of multiplicity. Proceeding onto the next step in the sequence relies upon rejecting H_0 in the previous step, a 'success'. Each step will only be considered confirmatory if all previous steps were 'successful'. If any of the previous steps were not successful, the tests of the subsequent steps have to be interpreted in an exploratory sense. This procedure allows testing each step at the two-sided alpha-level of 5%:

1. change from baseline in HbA1c at 24 weeks of treatment
2. change from baseline in mean 24-hour ambulatory SBP at 12 weeks of treatment
3. change from baseline in mean trough ambulatory SBP at 12 weeks of treatment
4. change from baseline in body weight in kg at week 24 of treatment
5. change from baseline in trough seated SBP at 12 weeks of treatment

Proprietary confidential information.

© 2016 Boehringer Ingelheim International GmbH or one or more of its affiliated companies. All rights reserved.

This document may not - in full or in part - be passed on, reproduced, published or otherwise used without prior written permission.

At each of the 5 stages of the hierarchical sequence the hypotheses will be tested as described below:

$H_{0,1}$: No difference in mean endpoint between empagliflozin and placebo

$H_{1,1}$: A difference in mean endpoint between empagliflozin and placebo

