10.2 BLOOD PRESSURE MEASUREMENT PROCEDURE

Blood pressure measurements are to be made per the [Flow Chart](#).

The preferred method for blood pressure measurement is standard mercury sphygmomanometry. If a standard mercury sphygmomanometer is not available, it is suggested that the investigator use <http://www.dableeducational.org> to determine if the device is recommended.

Initially, blood pressure should be taken 3 times in both arms. If the mean pressures differ by more than 10 mmHg, the arm with the higher pressure (systolic or – if needed, diastolic)

Proprietary confidential information.

© 2016 Boehringer Ingelheim International GmbH or one or more of its affiliated companies. All rights reserved.

This document may not - in full or in part - be passed on, reproduced, published or otherwise used without prior written permission.

should be used for subsequent measurements. If the pressures are ≤ 10 mmHg, the non-dominant arm should be used for subsequent measurements.

Blood pressure measurements should be performed on the same arm and, if possible, by the same person. The same method and type of device should be used throughout the trial, for a given patient. All blood pressure measurements should be performed approximately at the same time, i.e. in the morning prior to any blood being drawn or any study medication being taken.

After patients have rested quietly, in the seated position for two minutes, three blood pressure measurements will be taken approximately two minutes apart. The seated pulse rate will be taken during the two-minute interval between the second and third blood pressure reading.

Blood pressure measurements should be recorded to the nearest 2 mmHg only when measured with a manual sphygmomanometer; when digital devices are used the value from the device should be recorded to the nearest 1 mmHg and the pulse rate from the second measurement should be used.

For calculation of mean values, decimal places should be rounded to integers (e.g. a DBP of 94.5 would be rounded to 95 mmHg and a DBP of 109.4 would be rounded to 109 mmHg).

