10.3 ORTHOSTATIC BLOOD PRESSURE MEASUREMENT PROCEDURE

Orthostatic blood pressure measurements should be performed on the same arm as BP and ABPM and, if possible, by the same person. The same method and device must be used throughout the trial, for a given patient. All blood pressure measurements should be performed approximately at the same time, i.e. in the morning prior to any blood being drawn or any study medication being taken.

Procedure for Orthostatic Blood pressure:

1. Obtain the patient's pulse rate and BP while supine for 5 minutes
2. Record the readings
3. Have the patient stand.
4. Obtain the patient's pulse rate and BP every minute during the first 3 minutes while standing (1, 2 and 3 minutes)
5. Record the readings

If any one of the three pulse rates has increased by 20 BPM from the supine pulse rate or any one of the three systolic blood pressures has decreased by 20 mmHg from supine SBP, or any one of the three DBPs has decreased by 10 mmHg from supine DBP, orthostatic BP test is considered positive.

Proprietary confidential information.

© 2016 Boehringer Ingelheim International GmbH or one or more of its affiliated companies. All rights reserved.

This document may not - in full or in part - be passed on, reproduced, published or otherwise used without prior written permission.

If the patient is unable to stand, orthostatic BP test may be taken while the patient is sitting with feet dangling. If positive orthostatic BP test changes occur while sitting, DO NOT continue in the standing position.

Document the time and vital signs for supine and standing positions after 1, 2 and 3 minutes.

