5 ENDPOINT(S)

[figure not shown]
Note that several imputation methods will be used for the analysis of efficacy endpoints. Further details can be found in [Section 6.6](#).

Throughout the TSAP, the following should be considered:

- Successful is defined by the vendor BioClinica Inc. as a set of ambulatory blood pressure measurements (ABPM) readings meeting all of the following criteria:
 - Start time must be between 07:00 and 11:00
 - Minimum duration of 24 hours after beginning of the test
 - Minimum of 70% valid readings in the period
 - Total Required Hours is 18 (minimum valid readings for Required Hour is 1)
 - Total Exception Hours is 6 (minimum valid readings for Exception Hour is 0)
 - Total Consecutive Exception Hours is 2
- Valid is defined by the vendor BioClinica Inc. as a reading meeting all of the following criteria:
 - Systolic blood pressure (SBP) between 60 mmHg and 261 mmHg inclusive
 - Diastolic blood pressure (DBP) between 40 mmHg and 151 mmHg inclusive

- 
- Usable is defined as a reading within 24 hours of the beginning of test.
 - All ambulatory endpoints will be calculated by using successful, valid and usable ambulatory blood pressure (BP)/HR readings only. If any ambulatory BP/HR reading is not successful, valid or usable, then the corresponding ambulatory BP/HR measurements will also be set to not successful, valid or usable.
 - All 24-hour means are defined as the mean of hourly means (based on clocktime) of successful, valid and usable readings.
- 

- 
- Mean trough ambulatory BP is defined as the mean of successful, valid and usable readings measured from 22:00 until 23:59 hours after the beginning of the test.
 - Trough seated BP is defined as the mean of the seated/in office vital signs measurements including those taken after the removal of the ABPM device taken on the day of the clinic visit prior to trial drug intake.

- 
- PP is defined as (SBP - DBP).

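### Trough seated SBP (step V) mixes readings taken after 2 minutes and after at least 15 minutes of rest, and the visit instructions point sites to the wrong BP appendix

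*Protocol*

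**What the plan says.** Change from baseline in trough seated SBP at week 12 is the fifth and last step of the confirmatory hierarchy (Protocol 7.2: "5. change from baseline in trough seated SBP at 12 weeks of treatment").

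The general measurement rule, in Protocol 5.1.2 under seated blood pressure, is that BP "will be measured after 2 minutes of rest in the seated position", with three readings averaged. Appendix 10.2 repeats it: "After patients have rested quietly, in the seated position for two minutes, three blood pressure measurements will be taken approximately two minutes apart".

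On ABPM-removal days a longer rest applies. Under ABPM, section 5.1.2 says "the patient will be allowed rest for 15 minutes and a seated BP measurement (trough BP) will be taken". Flow chart footnote I and the instructions for Visits 2.2, 5.1 and 7.1 make it a minimum: "Allow the patient to rest for at least 15 minutes after the monitor is removed".

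Sections 6.2.1 and 6.2.2 allow Visits 3, 5.2 and 7.2 to be done on the removal day once the ABPM has succeeded, but do not require it.

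SAP section 5 defines trough seated BP as the mean of the in-office readings, "including those taken after the removal of the ABPM device taken on the day of the clinic visit prior to trial drug intake".

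For method, section 6.2.2 says of the whole treatment period: "For details regarding the correct method for measuring BP, please see [Appendix 10.3". Section 6.2.1 gives the same pointer for Visits 1 and 2.1. Appendix 10.3 is the orthostatic test, which begins "Obtain the patient's pulse rate and BP while supine for 5 minutes". The seated procedure is Appendix 10.2, as section 5.1.2 correctly cites.

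**The concern.** A change from baseline is cleanest when both values are taken under the same conditions. Here a patient seen for Visit 3 on a separate day has a baseline after 2 minutes of seated rest. If Visit 5.2 is then done on the removal day, the week-12 value is, or includes, a reading taken after at least 15 minutes. The reverse can also happen. Any effect of the longer rest on SBP then enters the change score as a product of scheduling.

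At stake is precision at step V and at the other seated BP endpoints: seated SBP at week 24, and seated DBP at weeks 12 and 24. The wrong pointer is a second, operational matter. A site that followed it literally would find supine and standing readings described, not the three seated readings that the endpoint needs.

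**Working it through.** **1. Which preparation applies where**

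| Reading | Rest stated | Source |
|---|---|---|
| Seated BP at clinic visits, including Visit 4 | 2 minutes, seated | Protocol 5.1.2, Appendix 10.2 |
| Trough seated BP after ABPM removal (Visits 2.2, 5.1, 7.1) | 15 minutes, or at least 15 minutes; posture not stated | Footnote I, 5.1.2, 6.2.1, 6.2.2 |

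The post-removal reading is itself labelled trough BP in section 5.1.2, so it is not a side measurement.

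**2. Which reading reaches the analysis**

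SAP 6.7 takes baseline as the last value before the first randomised dose. For week 12 it takes one observation in days 57 to 105, the closest to the planned day. If two fall on the same day it takes the first, yet SAP section 5 averages the in-office readings with the post-removal ones. When a visit set and a post-removal set share a day, the plan therefore does not say clearly which value enters step V. Nothing in the SAP separates the two rest conditions.

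**3. The plan's own power figure**

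Protocol 7.6 assumes a 5 mmHg difference with SD 10 for 24-hour ambulatory SBP, 64 evaluable per arm, two-sided 5%. The noncentrality is 5 / (10 × √(2/64)) = 2.83 on 126 degrees of freedom, and the two-sample t-test power is 80.15%. The stated 80% reproduces. It is a figure for ambulatory SBP; none is given for seated SBP.

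**4. Illustration of the possible loss**

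Assume that the longer rest shifts SBP by a constant d, that a fraction p of patients have the longer-rest reading at each of baseline and week 12, and that a patient's status at the two visits has correlation ρ. The variance added to the raw change is

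2 × d² × p(1−p) × (1−ρ).

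Borrowing the 5 mmHg and SD 10 above, at 64 per arm and with ρ = 0:

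| Assumed d (mmHg) | p = 0.25: SD, power | p = 0.5: SD, power |
|---|---|---|
| 2 | 10.07, 79.6% | 10.10, 79.4% |
| 4 | 10.30, 77.8% | 10.39, 77.1% |
| 6 | 10.65, 75.0% | 10.86, 73.4% |
| 8 | 11.14, 71.2% | 11.49, 68.5% |

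For example, d = 4 and p = 0.5 add 2 × 16 × 0.25 = 8, so SD = √108 = 10.39. With ρ = 1, meaning that each patient has the same scheduling at both visits, the added variance is zero and power stays at 80.1% whatever d is.

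Every input here except the α level and n = 64 is assumed or borrowed from another endpoint, so the table gives no estimate for step V.

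**5. The pointer**

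The amendment log lists the seated procedure as 10.3 (Amendments 1 and 3), whereas the current appendix numbers it 10.2. The references in 6.2.1 and 6.2.2 look like a number left uncorrected after renumbering.

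**The case against.** The strongest reply is that the two rests are not alternatives. The 15 minutes is a wait after device removal, and the seated reading that follows may still be preceded by the 2 minutes in Appendix 10.2. On that reading the rules stack and do not contradict each other. This stands: the defect is unequal total preparation, not a strict contradiction, and no document shows that the extra wait changes SBP.

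The power illustration is also open to attack, and the criticism is right. It borrows the effect and SD of 24-hour SBP. p = 0.5 maximises p(1−p). Independence between visits is doubtful, because a patient who needs the same-day option once may well need it again. The planned MMRM adjusts for baseline seated SBP, which dampens baseline noise, and averaging two same-day sets would dilute d.

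A reader might infer that the noise is site-dependent, and that with about 85 sites it cannot be modelled out. The documents do not support this. The Amendment 2 rationale for the same-day option concerns patients who cannot take several days off close together. Section 5.1.2 also requires the times of the seated reading and of the end of ABPM to be recorded, so removal-day readings can be identified for each patient.

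A reader might also infer that sites following Appendix 10.3 would omit seated readings. That is speculative: section 5.1.2 cites Appendix 10.2 correctly, the appendices are adjacent and clearly titled, and Visits 3, 5.2 and 7.2 list BP and the orthostatic test separately.

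**Conclusion.** The point holds as a modest, cheaply avoidable weakness. Readings under unequal preparation feed one confirmatory endpoint, scheduling decides which kind a patient contributes, and the SAP does not separate them. The method pointer in sections 6.2.1 and 6.2.2 is wrong.

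The consequence is a non-differential loss of precision at step V and the other seated BP endpoints. A reader might infer bias, but with blinded 1:1 randomisation there is no reason for scheduling to differ by arm. Steps I to IV do not use seated BP and are unaffected. Step V is confirmatory only if all four earlier steps succeed.

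The size is unknown. It depends on the effect of the longer rest, on how often each option is used and on how consistently, and the documents give none of these. They also give no effect, SD or power for seated SBP. The illustrated loss runs from zero to about 12 power points (80.1% to 68.5%), the upper end needing an assumed 8 mmHg shift, an even split and independent scheduling.

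**What to change.** - State one rest condition, including posture, for every trough seated BP reading (Visits 3, 4, 5.2 and 7.2, and after each ABPM removal), in the same words in Protocol 5.1.2, 6.2 and Appendix 10.2.
- Correct the pointers in 6.2.1 and 6.2.2 from Appendix 10.3 to Appendix 10.2.
- Have the SAP state which reading enters the analysis when a visit-day set and a post-removal set both exist, and reconcile the averaging in SAP section 5 with the first-value rule in SAP 6.7.
- Reconcile the timing text in 6.2.2, which places the ABPM 7 to 2 days before Visit 5.2 yet allows Visit 5.2 on the removal day.

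The cost is wording, plus some minutes per visit (about 13, from 15 − 2) if the longer rest is adopted.

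Changing only the SAP, by taking both values from the post-removal readings, is not an adequate substitute. It would conflict with the baseline and visit-selection rules in SAP 6.7, and it would leave Visit 4, which falls within the span of the step V repeated-measures model, under the 2-minute rule.
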